Official Title:

**Ultrasonography Versus Palpation for Spinal Anesthesia in
Obese Parturients Undergoing Cesarean Delivery**

ClinicalTrials.gov Identifier:

NCT03792191

Document Date:

31/12/2018

Introduction:

Neuraxial blocks (including single shot spinal, epidural, and combined spinal-epidural) are the most commonly used techniques for uncomplicated cesarean delivery to avoid the complications of general anesthesia such as airway and pulmonary complications.¹

Neuraxial anesthesia relies primarily on the visualization and palpation of the surface landmarks, which can be difficult in the setting of obesity, edema, and anatomical variation.²

Obesity causes difficulty in the detection of anatomical landmarks during neuraxial blocks resulting in increased number of attempts, longer procedure time, higher incidence of vascular puncture, and higher failure rate.³

Ultrasonography has been used to guide neuraxial blocks either as a prepuncture procedure or less commonly as a real-time technique. Ultrasonography is readily available, relatively safe, and has now been familiar for anesthesiologists being used in vascular access and various regional anesthetic techniques.^{4,5}

Prepuncture ultrasound scan has been utilized to identify the midline, locate the appropriate intervertebral space, detect the optimal angle for needle insertion, and measure the distance to the epidural space. This added information has increased the success rate of neuraxial block on the first attempt, increased patient comfort and satisfaction, and decreased the incidence of complications such as vascular puncture and backache.^{6,7} However, the use of ultrasonography for identification of spinal structures is complicated because the epidural and intrathecal spaces are a thin and deep structure and surrounded by bony structures

which impede the ultrasound beam. It also needs additional training and adds cost and time to the procedure.⁸

In obese patients, there are multiple factors that affect image quality because of deep anatomic location of structures, the ultrasound beam travels a greater distance, resulting in beam attenuation. Also phase aberration of the sound field occurs because of uneven speed of sound in the irregularly-shaped adipose layers. This is due to differing speeds of sound in the overlying nonhomogeneous tissues above the focus of the transducer. Another factor that can affect the quality of the ultrasound image is reflection which is due to mismatch of acoustic impedance at the fat/muscle interface. When the ultrasound beam crosses a boundary between muscle layer and fat, a portion of energy is reflected back to the transducer because of different acoustic velocity between the two tissues.⁹

Moreover, the real-time ultrasound guidance seems difficult and may need two physicians; one to hold the ultrasound probe and the other to perform the neuraxial block. Therefore, real-time ultrasound guided neuraxial blocks are not currently recommended for routine use.⁵ The first report of ultrasound utilization for epidural catheterization in the English literature was published by Cork et al. in 1980. There were very few reports on the topic until the last decade when increasing number of studies were performed due to the great innovation in ultrasound technology.² Most of these studies were designed to validate the prepuncture technique and they used inconsistent imaging strategies and were not blinded.

Several studies have examined the use of preprocedural ultrasonography for spinal anesthesia and compared it with the conventional landmark technique. Creaney et al have used ultrasonography to identify the lumbar spaces in parturients with poorly

defined landmarks presenting for cesarean delivery under spinal anesthesia and demonstrated that ultrasonography reduced the number of needle passes and did not prolong the whole procedure time.¹⁰ Ekinci et al compared ultrasonography with conventional landmark technique in parturients with impalpable anatomical landmarks.¹¹ Real-time ultrasonography also was used to guide spinal anesthesia in patients with predicted difficult anatomy.¹²

Aim of the study:

The aim of this study is to evaluate the efficacy of prepuncture ultrasonography to facilitate spinal anesthesia in obese parturients undergoing elective cesarean delivery compared with the conventional palpation technique.

Outcomes of the study:

The primary outcome will be the number of needle passes required to obtain free CSF flow. Secondary outcomes will be the number of skin punctures required to obtain free CSF flow, the success rate at the first needle pass, the success rate at the first skin puncture, the duration of the spinal procedure, patient satisfaction from the procedure, and the incidence of vascular puncture, paresthesia, failure to obtain CSF flow, and failed spinal block.

Anticipated Duration of the study:

18 months

Type of the study:

Prospective, randomized controlled, double-blind, 2-arm study.

The study subjects and the investigators assessing the outcomes will be blinded to the study group.

Patients:

The study will be conducted on parturients scheduled for elective cesarean delivery under spinal anesthesia at the Obstetric department of Mansoura University Hospitals.

Inclusion Criteria:

- American Society of Anesthesiologists physical status II-III parturients
- Full term, singleton pregnancy
- Body Mass Index ≥ 35 Kg/m²

Exclusion Criteria:

- Age < 19
- Women presenting in labor
- Contraindications to neuraxial anesthesia (Coagulopathy, increased intracranial pressure, or local skin infection)
- Significant spinal deformities or previous spinal surgery
- Preeclampsia

Methods:

After obtaining written informed consent, the study subjects will be randomly assigned to 2 equal groups (ultrasonography and palpation groups) according to computer-generated codes using the permuted block randomization method with randomly selected block sizes of 4 and 6. The group allocation will be concealed in sequentially numbered, sealed opaque envelopes.

Vascular access will be obtained then the subjects will be placed in the sitting position and standard monitors (electrocardiography, non-invasive blood pressure, and pulse oximetry) will be applied. The subjects will be kept in the same position during identification of landmarks and during the spinal anesthesia procedure. The subjects will be examined for the ease of landmark palpation using a 4-point scale (1 = the spinous processes and the interspaces can be identified by light palpation; 2 = the spinous processes and the interspaces can be identified by deep palpation; 3 = the spinous processes only can be identified by deep palpation, and the interspaces cannot be identified; 4 = neither the spinous processes nor the interspaces can be identified). The difficulty grade for each patient will be recorded.

In the palpation group, a sham procedure will be performed to blind the subjects by sliding the ultrasound probe on the patient's back while the ultrasound machine is in the freeze position. Conventional palpation technique will be performed: The midline will be identified by palpation of the spinous processes and the line connecting the iliac crests (Tuffier's line) will be assumed to cross the L4 spine or L3-L4 interspace. Identification of 2 intervertebral spaces (L3-L4 and L2-L3) will be done and the widest/most easily palpable interspace will be chosen for needle puncture. In women with impalpable spines, the iliac crest or the crease at

the bottom of the spine will be used to determine the needle insertion point.

In the ultrasonography group, a systematic 7–step approach will be performed using an 8-2 MHz curved array transducer (SonoAceR3[®], Samsung Medison; Seoul, South Korea):

1. The probe will be longitudinally placed on the bottom of the spine, with the probe mark pointing cephalad, to obtain the longitudinal view of the sacrum and the paramedian sagittal oblique view of the L5–S1 interspace.
2. The operator will count up the intervertebral levels to obtain the paramedian sagittal oblique view of the L3–L4 interspace.
3. The probe will be rotated 90° anticlockwise to obtain the transverse interlaminar view of the L3–L4 interspace, which will be used in the next steps.
4. The skin will be marked with horizontal and vertical lines at the midpoints of the probe's short and long sides, respectively; the intersection point of the 2 lines represents the needle insertion point.
5. The angle of the probe obtaining the best sonographic image will be observed.
6. The distance from the skin surface to the ventral aspect of the ligamentum flavum-dura mater complex will be measured; this will correspond to the depth of the epidural space.
7. The probe will be moved 1 interspace cephalad to obtain the transverse interlaminar view of the L2–L3 interspace and steps 4 to 6 will be repeated.

The interspace with the best sonographic image or the widest/ most easily palpable interspace will be chosen for the first attempt in the

ultrasonography and palpation groups, respectively. If the 2 spaces are of equal image quality or width/ease of palpation, the L3-L4 interspace will be first attempted. The puncture site will be infiltrated with 1-2 mL of 2% lidocaine. Spinal anesthesia will be performed with a 25- or 22-gauge spinal needle (a 22-gauge needle will be only used after a failed first attempt in subjects with tough ligaments) using a midline or paramedian approach according to the preference of the operator. The paramedian approach will be used in women having difficulty in flexing their spines and/or difficult interspaces; the puncture site is 1 cm lateral to and 0.5 cm below the midpoint of the interspace. After obtaining free cerebrospinal fluid (CSF) flow, 2.5 mL of 0.5% hyperbaric bupivacaine (12.5 mg) and fentanyl 15 µg will be intrathecally administered. After intrathecal injection, women will be placed supine with slight left lateral table tilt.

A maximum of 11 passes (the first attempt and 10 redirections) of the spinal needle will be allowed for each skin puncture and a maximum of 6 skin punctures will be allowed to obtain free CSF flow.

The number of performed needle passes (defined as any forward introduction of the spinal needle after its incomplete withdrawal, including the primary attempt) and skin punctures (defined as any separate skin puncture by the needle after its complete withdrawal, including the primary attempt) will be recorded.

The occurrence of unintentional vascular puncture will be recorded. The actual duration of the procedure (from the start of the first skin puncture by the spinal needle to obtaining free CSF flow) will be recorded.

Patient satisfaction from the procedure will be assessed immediately after intrathecal injection using a five-point scale (1 = very unsatisfied, 2 = unsatisfied, 3 = fair, 4 = satisfied, 5 = very satisfied).

The upper sensory level will be assessed using pin prick and surgery will start after attaining a level of T6 or higher. The level after 20 minutes of intrathecal injection will be recorded; a level below T6 will be considered a failed spinal block and the patient will be managed as appropriate.

Sample Size Calculation:

The primary outcome will be the number of needle passes required to obtain free CSF flow. In a pilot study performed on 20 obese parturients using the palpation technique, 8 ± 5 needle passes were required to successfully obtain free CSF flow. Assuming $\alpha = 0.05$ and $\beta = 0.1$ (power = 90%) and using the 2-tailed Student t test, 133 subjects will be required in each group to detect a difference of 2 needle passes between groups which is considered to be the minimal clinically important difference. To allow for subject dropouts, 140 subjects will be assigned to each group.

Statistical analysis:

Data will be analyzed using the R software (R Core Team; R Foundation for Statistical Computing, Vienna, Austria). Continuous data will be tested for normality using the histogram and the Kolmogorov-Smirnov test. Normally distributed data will be presented as mean \pm standard deviation and compared using the Student's t test. Non-normally distributed data will be presented as median (range) and compared using the Mann-Whitney U test. Categorical data will be presented as number (percentage) and compared using the chi-square test or Fisher's exact test. A P-value < 0.05 will be considered statistically significant.

References:

1. American Society of Anesthesiologists Committee on Standards and Practice Parameters. Practice Guidelines for Obstetric Anesthesia: An Updated Report by the American Society of Anesthesiologists Task Force on Obstetric Anesthesia and the Society for Obstetric Anesthesia and Perinatology. *Anesthesiology* 2016;124:270–300.
3. Lee A. Ultrasound in obstetric anesthesia. *Semin Perinatol* 2014;38:349–58.
4. Balki M. Locating the epidural space in obstetric patients—ultrasound a useful tool: continuing professional development. *Can J Anaesth* 2010;57:1111–26.

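### The primary test is valid and adequately powered, but it leaves out the palpation-difficulty grade recorded for every woman; prespecifying a grade-adjusted version would add power if the grade predicts needle passes

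*Combined protocol and SAP*

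**What the plan says.** The primary outcome is the number of needle passes needed to obtain free CSF flow. Before describing any arm-specific step, the Methods section has each woman graded from 1 (spinous processes and interspaces found by light palpation) to 4 (neither can be found), and adds: "The difficulty grade for each patient will be recorded".

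Two places suggest that the grade may be prognostic. The Introduction says: "Obesity causes difficulty in the detection of anatomical landmarks during neuraxial blocks resulting in increased number of attempts". The Methods section also gives the palpation group a separate way of choosing the insertion point, in the sentence that begins "In women with impalpable spines, the iliac crest or the crease at".

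The grade is not mentioned again. Randomisation uses permuted blocks of 4 and 6 and names no stratification factor. The Statistical analysis section sends continuous data, after a histogram and a Kolmogorov-Smirnov test, to Student's t test or the Mann-Whitney test. It names no covariate and plans no confidence interval.

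On allocation, the Methods section says: "The group allocation will be concealed in sequentially numbered, sealed opaque envelopes". It does not say when the envelope is opened relative to the grading.

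**The concern.** A baseline measure that predicts the outcome can be used in a randomised comparison to remove some of the between-patient variation. Here such a measure is already collected on every woman, is closely tied to the mechanism under study, and costs nothing to use. If the grade does predict needle passes, the planned test has less power than the same data allow. On the t-test route, an interval for the mean difference would also be wider than it need be.

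The 90% power figure rests on an SD from a pilot of 20 women and a true difference of exactly 2 passes. If the real difference is smaller, the power recovered by adjustment matters more.

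**Working it through.** **Inputs from the plan (Sample Size Calculation).** Palpation pilot: "8 ± 5 needle passes were required to successfully obtain free CSF flow". Two-sided α 0.05, power 90%, and "133 subjects will be required in each group to detect a difference of 2 needle passes". The number assigned is 140 per group.

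**Input not in the documents.** R², the share of variance in passes explained by the grade, is assumed to lie between 0 and 30%.

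**Step 1: the plan's own figure.** The standardised difference is 2/5 = 0.4. The exact two-sample t calculation gives 132.3 per group, so 133; power at 133 is 90.1%. The stated sample size is right. A 5% dropout allowance gives 133/0.95 = 140.

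**Step 2: t-test route with adjustment.** Adjustment leaves a residual SD of 5·√(1−R²). Then:
- standardised difference = 0.4/√(1−R²)
- 95% half-width = t × 5 × √(2/133) × √(1−R²), where 5 × √(2/133) = 0.613 and t ≈ 1.969
- equivalent unadjusted size per group = 133/(1−R²)

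| Assumed R² | Power at 133 per group | 95% half-width (passes) | Equivalent unadjusted n per group |
|---|---|---|---|
| 0 | 90.1% | 1.21 | 133 |
| 2% | 90.7% | 1.20 | 136 |
| 5% | 91.5% | 1.18 | 140 |
| 10% | 92.9% | 1.15 | 148 |
| 30% | 97.3% | 1.01 | 190 |

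An R² of 5% is therefore worth as much as analysing all 140 per group unadjusted. The closed form does not charge for estimating the grade effects. In simulation, adjustment with R² 0 cost 0.6 to 0.9 point of power on this route.

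**Step 3: both routes, by simulation.** Passes are counts of at least 1, since the definition is "any forward introduction of the spinal needle after its incomplete withdrawal, including the primary attempt". With a mean of 8 and an SD of 5, right skew is plausible, so the Mann-Whitney route needs its own check. The simulations used 133 per group, means of 8 and 6, SD 5 in both groups, an assumed grade split of 20/35/30/15%, and routing by Kolmogorov-Smirnov test. Power as planned, then grade-adjusted within the same route:

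| Assumed R² | Near-normal counts (about 2% of runs go to Mann-Whitney) | Right-skewed counts (99 to 100% go to Mann-Whitney) |
|---|---|---|
| 0 | 90.2%, 89.7% | 98.6%, 98.7% |
| 2% | 89.8%, 89.7% | 98.0%, 98.1% |
| 5% | 90.4%, 91.1% | 97.9%, 98.4% |
| 10% | 90.2%, 92.3% | 97.3%, 98.9% |
| 30% | 90.2%, 97.1% | 95.8%, 99.7% |

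Monte Carlo error is 0.3 to 0.4 point, so differences under about half a point are noise. Type I error with skewed counts was 4.4 to 5.2% as planned and 4.6 to 5.0% adjusted.

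**Step 4: sensitivity.**
- Skewed counts with a smaller ultrasonography SD of about 3.8, R² 10%: Mann-Whitney 91.7%, van Elteren 94.6%.
- True difference 1.5 passes, R² 20%, skewed counts, assumed grade split 20/30/30/20%: t test 69% to adjusted linear model 78%; Mann-Whitney 81% to van Elteren 94%.
- Grade matters only in the palpation group (R² 30% there; 30%/4 = 7.5% pooled): near-normal 89.8% to 91.2%; skewed 97.0% to 97.5%.

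**The case against.** The strongest reply is that nothing is wrong. An unadjusted comparison in a randomised trial is legitimate, and this one reaches its power target. The gains are modest unless R² is well above 5%, and no R² is given. The Introduction's statement is about obesity in general, whereas every woman here already meets "Body Mass Index ≥ 35 Kg/m²", so it does not show how far the grade separates women within that range. The separate rule for impalpable spines concerns the palpation group only, and in that scenario the gain is 1.4 points (near-normal) or about the noise limit (skewed). All of this stands. It makes the point a conditional improvement and not a correction.

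A second objection is that adjustment could do harm if the person grading already knows the allocation. This also stands. Grading is described after random assignment, and the documents do not time the opening of the envelope. The benefit depends on settling that order.

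Three stronger readings are tempting and are not supported:
- *The plan is underpowered or biased without the grade.* Step 1 shows otherwise on power, and omitting a baseline covariate does not bias a randomised comparison.
- *Every reported result would become more precise.* The van Elteren test gains power, but the reported medians are unchanged. A narrower interval arises only on the t-test route, and the plan does not currently report one.
- *With skewed counts, an adjusted mean regression should never replace a rank test.* With SD 5 in both groups, Mann-Whitney does have more power than an unadjusted Welch t test (98.2% against 89.7%). If the ultrasonography SD falls with its mean to about 3.8, the order reverses (93.1% against 96.1%). The documents give an SD for palpation only, so no general rule follows.

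**Conclusion.** The point holds as a matter of efficiency. The planned test is valid and meets 90% power on its own assumptions, but it sets aside a recorded baseline grade that the protocol's own reasoning makes plausibly prognostic.

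On the t-test route the gain at 133 per group is 1.4 points of power at R² 5%, 2.8 at 10% and 7.2 at 30%, with a correspondingly narrower interval. On the rank route, van Elteren also gained power at R² of 5% or more, both with equal SDs and with the smaller ultrasonography SD, although at 5% with equal SDs the gain was only about half a point. If the grade explains about 2% or less, there is essentially nothing to gain.

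These sizes rest on an assumed R², assumed grade splits and assumed count distributions, and on the grade being a true baseline measure. Confidence is medium. The change is worth making because it is nearly free, not because the trial fails without it.

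**What to change.** In the Statistical analysis section, prespecify the grade-adjusted counterpart of each planned test as the primary analysis:
- where the plan would use the t test, a linear model of needle passes on group and grade (4 levels), reporting the adjusted mean difference with a robust 95% confidence interval;
- where the plan would use Mann-Whitney, a van Elteren test stratified by grade, with medians reported as planned.

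State in advance how a grade with women in only one group is pooled with a neighbouring grade. Keep the unadjusted test as a supporting analysis. In the Methods section, state that the grade is recorded before the allocation envelope is opened. All of this should be fixed before any outcome is seen by group.

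The cost is some SAP wording and, at most, the order of two bedside steps. No extra patients, data or staff are needed. The downside is a slightly more complex analysis and, if the grade turns out not to be prognostic, under 1 point of power.

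### Does the needle-pass definition leave out the first advance at second and later skin punctures?

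*Combined protocol and SAP*

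**What the plan says.** Outcomes of the study and Sample Size Calculation both name the primary outcome: "The primary outcome will be the number of needle passes required to obtain free CSF flow". Methods permits no more than six skin punctures per woman and also limits the passes within each one: "A maximum of 11 passes (the first attempt and 10 redirections) of the spinal needle will be allowed for each skin puncture". The next sentence of Methods defines what is recorded: "needle passes (defined as any forward introduction of the spinal needle after its incomplete withdrawal, including the primary attempt", and, in parallel, "skin punctures (defined as any separate skin puncture by the needle after its complete withdrawal, including the primary attempt". Sample Size Calculation uses a palpation pilot of 20 women in which "8 ± 5 needle passes were required to successfully obtain free CSF flow", and sizes the trial to "detect a difference of 2 needle passes between groups which is considered to be the minimal clinically important difference". The secondary outcomes include "the success rate at the first needle pass, the success rate at the first skin puncture".

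**The concern.** A pass is tied to incomplete withdrawal and a new skin puncture to complete withdrawal. The first advance at puncture 2 or later follows complete withdrawal, so it is a pass only if the primary attempt means the first attempt at each puncture. The definition does not say so. In the parallel puncture definition the same phrase most naturally refers to the woman's first attempt, so one phrase seems to carry two meanings in one sentence.

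This matters because the variable is the primary outcome. If the first advance at later punctures were left out, the undercount would grow with the number of punctures. That number is itself a secondary outcome that ultrasound may change, so the omission need not cancel between arms. The text also does not state which rule produced the pilot mean and SD.

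**Working it through.** **Inputs.** From Methods: at most 11 passes per puncture (1 first attempt + 10 redirections) and at most 6 punctures. From Sample Size Calculation: SD 5, difference 2, two-sided alpha 0.05, power 90%, 133 per group, raised to 140.

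**1. The plan's own figure.** Normal approximation: n = 2 × (1.960 + 1.282)² × 5² / 2² = 131.3, so 132 per group. The exact two-sample t calculation gives 132.3, so 133, as stated. 133 / 0.95 = 140. Power at 133 per group is 0.901 by the t test (0.904 by the normal approximation).

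**2. The two counts.** For a woman with k punctures and r redirections in total:

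- first advance counted at each puncture: k + r
- first advance counted once per woman: 1 + r
- gap: k − 1

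At the limit r = 10k, the counts are 11k and 10k + 1:

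| Punctures | Per puncture | Once per woman | Gap |
|---|---|---|---|
| 1 | 11 | 11 | 0 |
| 2 | 22 | 21 | 1 |
| 3 | 33 | 31 | 2 |
| 4 | 44 | 41 | 3 |
| 5 | 55 | 51 | 4 |
| 6 | 66 | 61 | 5 |

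**3. Which reading the text supports.** The limit allows 11 passes at every puncture and builds the 11 from a first attempt and ten redirections. On the once-per-woman reading, puncture 2 onwards could never yield more than 10 passes. The outcome is also the number of passes needed to reach CSF. On the narrower reading, a woman whose CSF appeared on the first advance of her second puncture would have reached it by an advance that was not a pass. The per-puncture reading has neither difficulty.

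**4. Effect on the comparison if the narrower count were used.** Each arm's mean falls by its mean of (k − 1), so the group difference shifts by the between-arm difference in mean punctures. The shift can go either way. If ultrasound reduces punctures, the difference moves toward zero. If ultrasound led to more punctures with fewer redirections, it would gain. For example, 3 + 5 = 8 under ultrasound and 2 + 6 = 8 under palpation are equal full counts, but become 1 + 5 = 6 and 1 + 6 = 7.

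**5. Size, as illustration only.** The documents give no puncture distribution. Suppose the full-count difference is 2, the SD stays at 5, and ultrasound lowers mean punctures by 0.25, 0.5 or 1.0. The narrower count then shows 1.75, 1.5 or 1.0, with power at 133 per group of 0.81, 0.69 or 0.37 (normal approximation). These figures are probably too pessimistic: dropping the puncture component would probably reduce the SD too, since women who need more punctures tend to need more redirections.

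**6. Recovery.** Punctures are recorded separately, so a uniformly narrow count converts exactly: (1 + r) + (k − 1) = k + r. In the example above, 6 + 2 = 8 and 7 + 1 = 8.

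**The case for a change.** The strongest case for a change is that the limit is a procedural rule, while the definition is what staff apply when filling in the form, and nothing says that the first governs the second. If some recorders counted once per woman and others once per puncture, the full count could not be rebuilt. A clarifying phrase would cost almost nothing, and at three punctures the gap of 2 matches the whole target difference.

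Part of this stands. The definition does lack the words that would tie it to each puncture, and mixed recording would not be recoverable. But mixed recording requires some recorders to adopt a reading that contradicts the adjacent sentence. If that happened without regard to arm or puncture count, the expected shift would be only a fraction of the one in step 4.

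The comparison with the target difference does not stand. It sets one woman's counting gap against a difference between group means, whereas only the arm difference in mean punctures enters the comparison. The power loss in step 5 needs a trial count narrower than the one behind the target of 2, and the document uses the same term for both. First-pass success is not at risk, since pass 1 is the first advance of the first puncture on either reading. An analyst deriving it from the counts would require one pass and one puncture.

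**Conclusion.** No change follows. The wording is incomplete, but the sentence before it supplies the counting rule, and on that rule the definition and the limit agree at 11 passes per puncture and 66 per woman. The alternative reading lowers the count by 0 to 5 passes per woman and by nothing for women with one puncture. Its effect on the group comparison is the between-arm difference in mean punctures, which is unknown and could favour either arm. The 133 and 140 per group stand.

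This rests on two assumptions: that recorders apply one rule, which the adjacent limit makes likely, and that the pilot's 8 ± 5 and the target of 2 use the same count as the trial. The documents do not state the second outright, but they give no sign against it. This is a detail that those running the trial would be expected to fill sensibly, not a rule shown to give a wrong result.

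### The trial is sized on a 2-pass difference, but a normality check picks the primary test, and the Mann-Whitney branch plans no effect measure with a confidence interval to judge against 2

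*Combined protocol and SAP*

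**What the plan says.** Under Outcomes of the study and again under Sample Size Calculation: "The primary outcome will be the number of needle passes required to obtain free CSF flow".

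Sample Size Calculation takes its spread from 20 pilot patients managed by palpation, in whom "8 ± 5 needle passes were required to successfully obtain free CSF flow". It sets two-sided alpha 0.05 and power 90%, and continues: "using the 2-tailed Student t test, 133 subjects will be required in each group to detect a difference of 2 needle passes between groups". Of that difference it says: "which is considered to be the minimal clinically important difference". The 133 is raised to 140 per group for dropouts.

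Statistical analysis gives one general rule for all continuous variables: "Continuous data will be tested for normality using the histogram and the Kolmogorov-Smirnov test". Data judged normal are summarised by mean and SD and compared by Student's t test. Otherwise: "Non-normally distributed data will be presented as median (range) and compared using the Mann-Whitney U test". The only decision criterion is: "A P-value < 0.05 will be considered statistically significant". Neither branch plans a between-group difference or a CI, and no rule is specific to the primary outcome.

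**The concern.** The design asks a question in passes: is the saving at least about 2? Two features of the analysis stop it from answering that question reliably.

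First, the primary test is not fixed. The trial's own data choose between a comparison of means and a rank comparison, and these target different quantities unless one arm is a pure shift of the other.

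Second, the branches differ in what can be recovered from the report. After the t test, a mean difference and its CI follow from the two means, SDs and group sizes, even though the plan does not ask for them. After Mann-Whitney, median (range) and a P-value give no route to a CI. A significant result could then reflect a saving well under 2 passes or well over it, and a non-significant one would not show which savings remain compatible with the data.

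**Working it through.** **1. Reproduce the sample size.** Inputs from Sample Size Calculation: difference 2, SD 5, two-sided alpha 0.05, power 0.90.

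Normal approximation: n = 2(1.960 + 1.282)² × 5² / 2² = 131.3, so 132 per arm. The exact t calculation gives 132.3, so 133, with power 90.1%. Also 133 / 0.95 = 140. The stated figures reproduce.

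**2. Which branch is likely?** The count cannot be below 1. The limits in Methods (11 passes per puncture, 6 punctures) cap it at 66. A normal curve with mean 8 and SD 5 puts Φ((1 − 8)/5) = Φ(−1.4) = 8% of its mass below 1, so some right skew is plausible. The documents do not give the shape, so shapes were assumed and simulated at 133 per arm. The Kolmogorov-Smirnov test used estimated mean and SD without correction, and rejection in either arm led to Mann-Whitney. The histogram part of the check was not simulated.

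- Negative binomial counts: 93-100% of trials entered the Mann-Whitney branch across repeated runs.
- Rounded truncated-normal counts: 67% (8 ± 5 vs 8 ± 5), 82% (8 ± 5 vs 6 ± 3.75) and 47% (8 ± 5 vs 8 ± 3.5).

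**3. Power at means 8 vs 6.** Over these shapes, with ultrasonography SD 5 or 3.75 (assumed): t test about 89-96%, Mann-Whitney 90-99%, the planned rule 91-99%.

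**4. What the Mann-Whitney output says about 2 passes.** With a true mean difference of 2, the difference in sample medians ran from 1 to 3 (ultrasonography SD 3.75) or 1 to 4 (SD 5) between its 5th and 95th percentiles. The Hodges-Lehmann shift averaged about 1.6 and 2.0 respectively, so it need not equal the mean difference.

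**5. What a CI would add.** Half-width = 1.969 × √[(SD₁² + SD₂²)/133].

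- SD 5 and 5: 1.969 × 0.613 = 1.21 passes.
- SD 5 and 3.75: 1.969 × 0.542 = 1.07 passes.

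Both are narrow enough to be useful against 2. Simulated Welch coverage was 94-96%.

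**6. Error rate.** With identical arms (8 ± 5), the planned rule rejected in 5.1% of negative binomial trials and 6.2% of truncated-normal trials (Monte Carlo SE 0.6 points). With equal means of 8 but unequal spread, negative binomial, it rejected in 8-9% at SD 5 vs 4.25 or 5.75, and in 17-19% at SD 5 vs 3.5 or 6.5. The truncated-normal figure at SD 5 vs 3.5 was 11%. The t test stayed at 4.5-5.0% in these unequal-spread scenarios.

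**7. Sensitivity of the mean to a few extreme counts.** The documents give no rate of failure to obtain CSF. Assume that a share p of women in each arm fail after 30-66 performed passes (uniform: mean 48, variance (37² − 1)/12 = 114), and that the rest follow the design figures. Arm variance = (1 − p)SD² + 114p + p(1 − p)(48 − mean)².

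Worst case, p = 2%, SD 5/5:

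- Variances 24.5 + 2.28 + 31.36 = 58.1 and 24.5 + 2.28 + 34.57 = 61.4.
- SE = √(119.5/133) = 0.948; difference = 0.98 × 2 = 1.96.
- Power ≈ Φ(1.96/0.948 − 1.969) = Φ(0.10) = 54%.

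Best case, p = 0.5%, SD 5/3.75: variances 33.4 and 23.3, SE 0.653, difference 1.99, power ≈ Φ(1.08) = 86%.

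Simulation (6,000 trials per scenario), SD 5/5 then SD 5/3.75:

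| Failure share | Welch power | Mann-Whitney power | CI half-width (passes) |
|---|---|---|---|
| 0.5% | 79%, 86% | 98%, 93% | 1.39, 1.27 |
| 1% | 70%, 76% | 98%, 92% | 1.56, 1.45 |
| 2% | 56%, 60% | 98%, 92% | 1.85, 1.76 |

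**The case against.** The best defence is that Mann-Whitney suits a skewed count, power is adequate, both medians are reported in passes, and the sponsor holds every individual count and could calculate an interval at any time. Most of this stands. The rank test is a reasonable choice, and step 7 shows that it resists a few extreme counts better than a comparison of means. What the defence does not supply is a named effect measure or a planned interval. A reader given only the planned summary cannot construct one, and Mann-Whitney does not test the difference between the medians.

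Four stronger readings are tempting and not supported:

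- *The trial is underpowered or wrongly sized.* The 133 reproduces, and power under the planned rule is at least about 90% in the scenarios of step 3.
- *The gate inflates false claims for ultrasonography.* Error is about 5% when the technique changes nothing. The higher rates need unequal spreads that the documents do not give, and the plan does not state equal means as its null hypothesis. Direction matters too: with equal means and ultrasonography SD 3.5, at most about 0.3% of trials were significant in favour of ultrasonography. The rejections point the other way, and the reverse holds if ultrasonography is the more variable arm.
- *The t test must therefore be primary.* It matches the sizing target, but its power could drop to about 54-86% under the failure shares assumed above. That is a trade-off for the sponsor.
- *A CI would settle a non-significant result.* Given a non-significant t-type P-value, it excludes a 2-pass saving in 92% of trials at a true saving of 0, 58% at 1 and 25% at 2 with SD 5/5, but in 98%, 82% and 58% with SD 5/3.75. What it shows depends on the unknown spread.

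**Conclusion.** The point holds as a cheap improvement of minor to moderate weight. The text alone establishes three things: the sizing target is 2 passes, the trial data choose the primary test, and the Mann-Whitney branch defines no effect measure and no CI. How likely that branch is depends on assumed shapes, since the documents give only a pilot mean and SD from one technique. It is near certain for clearly skewed counts and roughly even to likely for milder ones. If the arms differ in spread, a Mann-Whitney P-value may not reflect a saving in mean passes, and the direction of the discrepancy depends on which arm is more variable. Nothing here questions the number of women or the validity of Mann-Whitney as a test of identical distributions.

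**What to change.** For the primary outcome, remove the normality check and name one test in advance. Mann-Whitney is acceptable and robust to a few very high counts. Welch's t test matches the sizing target but carries the power risk shown in step 7. The sponsor should choose with that risk in view.

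Keep the estimate separate from the choice of test. Whichever test is named, plan to report:

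- the between-group difference in mean passes with a 95% CI (Welch or bootstrap), read against 2 passes;
- the Hodges-Lehmann shift with its 95% CI beside it.

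The cost is a few sentences. The sample size and the data collected do not change, because pass counts are already recorded for each woman. The data-driven choice of test is given up. The CI for the mean difference also widens, from a half-width of about 1.1-1.2 passes to as much as about 1.9 under the assumed failure shares, if a few women need very many passes. How to code women in whom CSF flow is not obtained is a separate issue.
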